### 7.8 X-Rays

| Variable (CRF annotation)          | How to be presented                                  |
|------------------------------------|--|
| Chest X-ray taken (XRCYN)          | # patients and % /category
(2 categories: Yes/No) |
| Chest X-ray Date (XRCDT)           | Listing only   |
| Hands and feet X-ray taken (XRHF)  | # patients and % /category
(2 categories: Yes/No) |
| Hands and feet X-ray Date (XRHFDT) | Listing only   |

## 7.9 Laboratory Assessments

## 7.9.1 Haematology

| Variable (CRF annotation)                                       | How to be presented  |
|---|--|
| Blood sample collected for analysis of
Haematology (BLHPERF) | <pre># patients and % /category, by visit (2 categories: Yes/No)</pre> |
| Haematology sample Date (BLHDT)                                 | Listing only   |
| Haematology sample Time (BLHTM)                                 | Listing only   |

Study SynAct-CS002 – Statistical Analysis Plan

| HbA1c, collected unit  (HBA1C, HBA1C_U)                                     | Listing only (units converted to mmol/L)   |
|---|--|
| HbA1c, mmol/mol (derived from HBA1C above)  | n, mean, sd, median, min, max, by visit  |
| HbA1c, Out of range and Clinically significantly abnormal (HBA1C_OR, HBA1C_CS)          | # patients and % /category
(1 category HBA1C_OR; Yes, 2 categories
HBA1C_CS; Yes/No), by visit |
| White blood cell, collected unit (WBCC, WBCC_U)   | Listing only (units converted to 10E9/L)   |
| White blood cell, 10E9/L (derived from WBCC above)                                      | n, mean, sd, median, min, max, by visit  |
| White blood cell, Out of range and Clinically significantly abnormal (WBCC_OR, WBCC_CS) | # patients and % /category
(1 category WBCC_OR; Yes, 2 categories
WBCC_CS; Yes/No), by visit   |
| Neutrophils, collected unit (NEUT, NEUT_U)  | Listing only (units converted to 10E9/L)   |
| Neutrophils, 10E9/L (derived from NEUT above)   | n, mean, sd, median, min, max, by visit  |
| Neutrophils, Out of range and Clinically significantly abnormal (NEUT_OR, NEUT_CS)      | # patients and % /category
(1 category NEUT_OR; Yes, 2 categories
NEUT_CS; Yes/No), by visit   |
| Lymphocytes, collected unit (LYMPO, LYMPO_U)  | Listing only (units converted to 10E9/L)   |
| Lymphocytes, 10E9/L (derived from LYMPO above)  | n, mean, sd, median, min, max, by visit  |
| Lymphocytes, Out of range and Clinically significantly abnormal (LYMPO_OR, LYMPO_CS)    | # patients and % /category
(1 category LYMPO_OR; Yes, 2 categories
LYMPO_CS; Yes/No), by visit |
| Monocytes, collected unit (MONOC, MONOC_U)  | Listing only (units converted to 10E9/L)   |
| Monocytes, 10E9/L (derived from MONOC above)  | n, mean, sd, median, min, max, by visit  |
| Monocytes, Out of range and Clinically significantly abnormal (MONOC_OR, MONOC_CS)      | # patients and % /category
(1 category MONOC_OR; Yes, 2 categories
MONOC_CS; Yes/No), by visit |
| Eosinophils, collected unit (EOSIN, EOSIN_U)  | Listing only (units converted to 10E9/L)   |
| Eosinophils, 10E9/L (derived from EOSIN above)  | n, mean, sd, median, min, max, by visit  |
|   |  |

| Eosinophils, Out of range and Clinically significantly abnormal (EOSIN_OR, EOSIN_CS)       | # patients and % /category
(1 category EOSIN_OR; Yes, 2 categories
EOSIN_CS; Yes/No), by visit |
|--|--|
| Basophils, collected unit (BASO, BASO_U)   | Listing only (units converted to 10E9/L)   |
| Basophils, 10E9/L (derived from BASO above)  | n, mean, sd, median, min, max, by visit  |
| Basophils, Out of range and Clinically significantly abnormal (BASO_OR, BASO_CS)           | # patients and % /category
(1 category BASO_OR; Yes, 2 categories
BASO_CS; Yes/No), by visit   |
| Hemoglobin, collected unit (HB, HB_U)  | Listing only (units converted to mmol/L)   |
| Hemoglobin, mmol /L (derived from HB above)  | n, mean, sd, median, min, max, by visit  |
| Hemoglobin, Out of range and Clinically significantly abnormal (HB_OR, HB_CS)              | <pre># patients and % /category (1 category HB_OR; Yes, 2 categories HB_CS; Yes/No), by visit</pre>  |
| Red blood cells (RBC), collected unit (RBC, RBC_U)   | Listing only (units converted to 10E12/L)  |
| Red blood cells (RBC), 10E12/L (derived from RBC above)                                    | n, mean, sd, median, min, max, by visit  |
| Red blood cells (RBC), Out of range and Clinically significantly abnormal (RBC_OR, RBC_CS) | # patients and % /category
(1 category RBC_OR; Yes, 2 categories
RBC_CS; Yes/No), by visit     |
| Thrombocytes, collected unit (THRC, THRC_U)  | Listing only (units converted to 10E9/L)   |
| Thrombocytes, 10E9/L (derived from THRC above)   | n, mean, sd, median, min, max, by visit  |
| Thrombocytes, Out of range and Clinically significantly abnormal (THRC_OR, THRC_CS)        | # patients and % /category
(1 category THRC_OR; Yes, 2 categories
THRC_CS; Yes/No), by visit   |

 Different laboratories might use different units. All values collected in different units than the units to be used for analysis will be converted, see section 3.6.

#### 7.9.2 Biochemistry

| Variable (CRF annotation) | How to be presented |
|---------------------------|---------------------|
|---------------------------|---------------------|

Study SynAct-CS002 – Statistical Analysis Plan

|   | 1   |
|---|---|
| Blood sample collected for analysis of
Biochemistry (BLBPERF)  | # patients and % /category, by visit
(2 categories: Yes/No)  |
| Biochemistry sample Date (BLBDT)  | Listing only  |
| Biochemistry sample Time (BLBTM)  | Listing only  |
| Alanine transaminase (ALT), collected unit  (ALT, ALT_U)                                    | Listing only (units converted to U/L)   |
| Alanine transaminase (ALT), U/L (derived from ALT above)  | n, mean, sd, median, min, max, by visit   |
| Alanine transaminase (ALT), Out of range and
Clinically significantly abnormal (ALT_OR, ALT_CS)      | <pre># patients and % /category (1 category ALT_OR; Yes, 2 categories ALT_CS; Yes/No), by visit</pre> |
| Aspartate transaminase (AST), collected unit
(AST, AST_U)  | Listing only (units converted to U/L)   |
| Aspartate transaminase (AST), U/L (derived from AST above)  | n, mean, sd, median, min, max, by visit   |
| Aspartate transaminase (AST), Out of range and
Clinically significantly abnormal (AST_OR,
AST_CS) | <pre># patients and % /category (1 category AST_OR; Yes, 2 categories AST_CS; Yes/No), by visit</pre> |
| γ–glutamyltransferase (GGT), collected unit (GGT,
GGT_U)   | Listing only (units converted to U/L)   |
| γ–glutamyltransferase (GGT), U/L (derived from
GGT above)  | n, mean, sd, median, min, max, by visit   |
| γ–glutamyltransferase (GGT), Out of range and
Clinically significantly abnormal (GGT_OR,
GGT_CS)  | # patients and % /category
(1 category GGT_OR; Yes, 2 categories
GGT_CS; Yes/No), by visit      |
| Bilirubin (total), collected unit (BILIT, BILIT_U)  | Listing only (units converted to µmol/L)  |
| Bilirubin (total), μmol/L (derived from BILIT
above)   | n, mean, sd, median, min, max, by visit   |
| Bilirubin (total), Out of range and Clinically significantly abnormal (BILIT_OR, BILIT_CS)              | # patients and % /category
(1 category BILIT_OR; Yes, 2 categories
BILIT_CS; Yes/No), by visit  |

Study SynAct-CS002 – Statistical Analysis Plan

| Bilirubin (conjugated), collected unit (BILIC,
BILIC_U)  | Listing only (units converted to $\mu$ mol/L)  |
|---|--|
| Bilirubin (conjugated), μmol/L (converted from
BILIC above)  | n, mean, sd, median, min, max, by visit  |
| Bilirubin (conjugated), Out of range and Clinically significantly abnormal (BILIC_OR, BILIC_CS)           | # patients and % /category
(1 category BILIC_OR; Yes, 2 categories
BILIC_CS; Yes/No), by visit   |
| Bilirubin (unconjugated), μmol/L, calculated
(BILICALC)  | n, mean, sd, median, min, max, by visit  |
| Bilirubin (unconjugated), Out of range and
Clinically significantly abnormal (BILIUN_OR,
BILIUN_CS) | # patients and % /category
(1 category BILIUN_OR; Yes, 2 categories
BILIUN_CS; Yes/No), by visit |
| Alkaline phosphatase (ALP), collected unit (ALP, ALP_U)   | Listing only (units converted to U/L)  |
| Alkaline phosphatase (ALP), U/L (derived from ALP above)  | n, mean, sd, median, min, max, by visit  |
| Alkaline phosphatase (ALP), Out of range and
Clinically significantly abnormal (ALP_OR,
ALP_CS)     | # patients and % /category
(1 category ALP_OR; Yes, 2 categories ALP_CS;
Yes/No), by visit       |
| Glucose (non-fasting), collected unit (GLUC,
GLUC_U)   | Listing only (units converted to mmol/L)   |
| Glucose (non-fasting), mmol/L (derived from GLUC above)   | n, mean, sd, median, min, max, by visit  |
| Glucose (non-fasting), Out of range and Clinically significantly abnormal (GLUC_OR, GLUC_CS)              | # patients and % /category
(1 category GLUC_OR; Yes, 2 categories
GLUC_CS; Yes/No), by visit     |
| Potassium, collected unit (POT, POT_U)  | Listing only (units converted to mmol/L)   |
| Potassium, mmol/L (derived from POT above)  | n, mean, sd, median, min, max, by visit  |
| Potassium, Out of range and Clinically significantly abnormal (POT_OR, POT_CS)                            | # patients and % /category
(1 category POT_OR; Yes, 2 categories
POT_CS; Yes/No), by visit       |
| Sodium, collected unit (SOD, SOD_U)   | Listing only (units converted to mmol/L)   |

| Sodium, mmol/L (derived from SOD above)   | n, mean, sd, median, min, max, by visit   |
|---|---|
| Sodium, Out of range and Clinically significantly abnormal (SOD_OR, SOD_CS)                         | <pre># patients and % /category (1 category SOD_OR; Yes, 2 categories SOD_CS; Yes/No), by visit</pre>   |
| Chloride, collected unit (CHLOR, CHLOR_U)   | Listing only (units converted to mmol/L)  |
| Chloride, mmol/L (derived from CHLOR above)   | n, mean, sd, median, min, max, by visit   |
| Chloride, Out of range and Clinically significantly abnormal (CHLOR_OR, CHLOR_CS)                   | # patients and % /category
(1 category CHLOR_OR; Yes, 2 categories
CHLOR_CS; Yes/No), by visit    |
| Calcium, collected unit (CALC, CALC_U)  | Listing only (units converted to mmol/L)  |
| Calcium, mmol/L (derived from CALC above)   | n, mean, sd, median, min, max, by visit   |
| Calcium, Out of range and Clinically significantly abnormal (CALC_OR, CALC_CS)                      | <pre># patients and % /category (1 category CALC_OR; Yes, 2 categories CALC_CS; Yes/No), by visit</pre> |
| Albumin, collected unit (ALB, ALB_U)  | Listing only (units converted to g/L)   |
| Albumin, g/L (derived from ALB above)   | n, mean, sd, median, min, max, by visit   |
| Albumin, Out of range and Clinically significantly abnormal (ALB_OR, ALB_CS)                        | <pre># patients and % /category (1 category ALB_OR; Yes, 2 categories ALB_CS; Yes/No), by visit</pre>   |
| Creatinine, collected unit (CREA, CREA_U)   | Listing only (units converted to цmol/L)  |
| Creatinine, цmol/L (derived from CREA above)  | n, mean, sd, median, min, max, by visit   |
| Creatinine, Out of range and Clinically significantly abnormal (CREA_OR, CREA_CS)                   | # patients and % /category
(1 category CREA_OR; Yes, 2 categories
CREA_CS; Yes/No), by visit      |
| C-Reactive Protein (CRP), collected unit (CRP,
CRP_U)  | Listing only (units converted to mg/L)  |
| C-Reactive Protein (CRP), mg/L (derived from CRP above)   | Presented with Secondary Efficacy Variables   |
| C-Reactive Protein (CRP), Out of range and
Clinically significantly abnormal (CRP_OR,
CRP_CS) | <pre># patients and % /category (1 category CRP_OR; Yes, 2 categories CRP_CS; Yes/No), by visit</pre>   |

| Urea, collected unit (UREA, UREA_U)   | Listing only (units converted to mmol/L)  |
|---|---|
| Urea, mmol/L (derived from UREA above)                                      | n, mean, sd, median, min, max, by visit   |
| Urea, Out of range and Clinically significantly abnormal (UREA_OR, UREA_CS) | # patients and % /category
(1 category UREA_OR; Yes, 2 categories
UREA_CS; Yes/No), by visit    |
| INR (INR)   | n, mean, sd, median, min, max, by visit   |
| INR, Out of range and Clinically significantly abnormal (INR_OR, INR_CS)    | <pre># patients and % /category (1 category INR_OR; Yes, 2 categories INR_CS; Yes/No), by visit</pre> |

 Different laboratories might use different units. All values collected in different units than the units to be used for analysis will be converted, see section 3.6.

## 7.9.3 Thyroid Function

| Variable (CRF annotation)   | How to be presented   |
|---|---|
| TSH, collected unit  (TSH, TSH_U)                                 | Listing only (units converted to 10E3/L)  |
| TSH, 10E3/L (derived from TSH above)  | n, mean, sd, median, min, max, by visit   |
| TSH, Out of range and Clinically significantly abnormal (TSH_OR, TSH_CS)      | # patients and % /category
(1 category TSH_OR; Yes, 2 categories TSH_CS;
Yes/No), by visit      |
| Total T3, collected unit (TT3, TT3_U)   | Listing only (units converted to nmol/L)  |
| Total T3, nmol/L (derived from TT3 above)                                     | n, mean, sd, median, min, max, by visit   |
| Total T3, Out of range and Clinically significantly abnormal (TT3_OR, TT3_CS) | <pre># patients and % /category (1 category TT3_OR; Yes, 2 categories TT3_CS; Yes/No), by visit</pre> |
| Free T3, collected unit (FT3, FT3_U)  | Listing only (units converted to pmol/L)  |
| Free T3, pmol/L (derived from FT3 above)                                      | n, mean, sd, median, min, max, by visit   |

Study SynAct-CS002 – Statistical Analysis Plan

| Free T3, Out of range and Clinically significantly abnormal (FT3_OR, FT3_CS)  | <pre># patients and % /category (1 category FT3_OR; Yes, 2 categories FT3_CS; Yes/No), by visit</pre> |
|---|---|
| Total T4, collected unit (TT4, TT4_U)   | Listing only (units converted to nmol/L)  |
| Total T4, nmol/L (derived from TT4 above)                                     | n, mean, sd, median, min, max, by visit   |
| Total T4, Out of range and Clinically significantly abnormal (TT4_OR, TT4_CS) | <pre># patients and % /category (1 category TT4_OR; Yes, 2 categories TT4_CS; Yes/No), by visit</pre> |
| Free T4, collected unit (FT4, FT4_U)  | Listing only (units converted to pmol/L)  |
| Free T4, pmol/L (derived from FT4 above)                                      | n, mean, sd, median, min, max, by visit   |
| Free T4, Out of range and Clinically significantly abnormal (FT4_OR, FT4_CS)  | # patients and % /category
(1 category FT4_OR; Yes, 2 categories FT4_CS;
Yes/No), by visit      |

 Different laboratories might use different units. All values collected in different units than the units to be used for analysis will be converted, see section 3.6.

## 7.9.4 Urinalysis

| Variable (CRF annotation)                    | How to be presented  |
|--|--|
| Urine sample collected for analysis (UAPERF) | <pre># patients and % /category, by visit (2 categories: Yes/No)</pre>                           |
| Urine sample Date (UADT)                     | Listing only   |
| Urine sample Time (UATM)                     | Listing only   |
| Urinalysis result Blood (UABLOOD)            | 

# patients and % /category, by visit

(2 categories: Negative/Positive)

 |
| Urinalysis result Protein (UAPROT)           | 

# patients and % /category, by visit

(2 categories: Negative/Positive)

 |
| Urinalysis result Glucose (UAGLUC)           | 

# patients and % /category, by visit

(2 categories: Negative/Positive)

 |
| Sample sent for urine culture (UCULTYN)      | <pre># patients and % /category, by visit (2 categories: Yes/No)</pre>                           |

| Urine culture result (UCULTRES)                | # patients and % /category, by visit
(Categories to be based on text entries) |
|--|--|
| Urine culture clinically significant (UCULTCS) | # patients and % /category, by visit
(2 categories: Yes/No)                   |

## 7.9.5 Serology

| Variable (CRF annotation)                     | How to be presented   |
|---|---|
| Serology blood sample collected (BLSYN)       | <pre># patients and % /category (2 categories: Yes/No)</pre>                                    |
| Serology blood sample Date (BLSDT)            | Listing only  |
| Rheumatoid Factor (RF) Test result (RF, RFND) | <pre># patients and % /category (3 categories: Negative/Positive/Not done)</pre>                |
| Anti-CCP Test result (ACCP, ACCPND)           | <pre># patients and % /category (3 categories: Negative/Positive/Not done)</pre>                |
| HBsAg Test result (HBSAG)                     | <pre># patients and % /category (3 categories: Negative/Positive/Not done)</pre>                |
| HBV antibody Test result (HBVANTI)            | <pre># patients and % /category (3 categories: Negative/Positive/Not done)</pre>                |
| HCV antibody Test result (HCVANTI)            | 

# patients and % /category

(3 categories: Negative/Positive/Not done)

 |

### 7.9.6 MC1R Genotype Analysis

| Variable (CRF annotation) | How to be presented  |
|---------------------------|--|
| Blood sample Date         | Listing only   |
| MC1R genotype result      | <pre># patients and % /category (2 categories: MC1R Present/Not present)</pre> |

## 7.10 Adverse Events

| Variable (CRF annotation)               | How to be presented  |
|---|--|
| Any new (or changes to) AE (AEYN)       | # patients and % /category
(2 categories: Yes/No), by visit   |
| AE description/Term (AETERM)            | Listing only (used for MedDRA coding)  |
| AE MedDRA term (coding performed by DM) | # patients and % /MedDRA term
(x categories), by visit  |
| AE start date (AESTDAT)                 | Listing only   |
| AE end date (AEENDAT)                   | Listing only   |
| AE ongoing (AEONG)                      | Listing only   |
| Date site aware of AE (AEAWDT)          | Listing only   |
| AE severity (AESEV)                     | <pre># patients and % /category (5 categories: Mild/Moderate/Severe/Life- threatening/Death), by visit</pre>   |
| Relationship to study treatment (AEREL) | # patients and % /category
(5 categories: Definitely not related/Probably
not related/Possibly related/Probably
related/Definitely related), by visit   |
| Action taken with study drug (AEACT)    | # patients and % /category
(5 categories: Dose not changed/Dose
interrupted/Drug withdrawn/Not applicable/
Unknown), by visit   |
| AE outcome (AEOUT)                      | 
 
# patients and % /category
 
(6 categories: Fatal, Not recovered/Not
Resolved, Recovered/Resolved,
 
Recovered/Resolved with sequelae,
 
Recovering/Resolving
 
Unknown), by visit
 
 |
| Medication given to treat AE (AETREAT)  | # patients and % /category
(2 categories: Yes/No), by visit   |

| Serious Adverse Event (AESER, AESER1, AESER2, AESER3, AESER4, AESER5, AESER6) | 
 
# patients and % /category
 
(2 categories for AESER: Yes/No, plus number of
each kind of SAE: Death, Life-threatening,
Inpatient hospitalisation or prolongation of
existing hospitalisation, Persistent or significant
disability/incapacity, Congenital anomaly or
birth defect, and/or Important medical event),
by visit
 
 |
|---|--|
| SAE report Date (SAEREPDT)  | Listing only   |
| Date of birth (BRTHDT)  | Listing only   |
| Sex (GENDER)  | Listing only   |
| Height, cm (HEIGHT, AE dataset)   | Listing only   |
| Weight, kg (SAEWGHT)  | Listing only   |
| SAE description (SAEDESC)   | Included in SAE table  |
| Phase of study at time of event (SAESP)                                       | # patients and % /category (4 categories:
Screening/Treatment/Wash-out/Follow-up),
included in SAE table   |
| Study Drug Information (SAESD, SAEFREQ, SAEFADT, SAELADT)                     | Listing only   |
| SAE abate after stopping study medication (SAEDECH)                           | Listing only   |
| SAE reappear after reintroduction of study medication (SAERECH)               | Listing only   |
| Blinding code broken (SAEBBROK, SAEBBDT)                                      | Listing only   |
| Concomitant medication (SAECM)  | Listing only   |
| Relevant medical history (SAEMH)  | Listing only   |
| Hospitalisation Details (SAEHOSP, SAEADT, SAEDDT)                             | Listing only   |
| Death Details (SAEDEDT, SAEPCAUS, SAEAUTO, SAEINF)                            | Listing only   |

The incidence of AEs will be summarized by the reported AE term. A subject will be counted only once in the incidence count for a specific AE term, although an AE term might be reported more than once for a particular subject.

Separate summaries will be provided for relationship (yes, no) to study drug. An AE will be considered related to study drug if the investigator reported the event to be "definitely, probably, possibly, or unlikely" related to treatment on the CRF.

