24.6 Data processing and quality Control

The designated CRO will be responsible for data processing and quality control. Data management will be carried out as described in the CRO's standard operating procedures, which includes the generation and resolution of manual electronic data queries.

All planned data management procedures will be documented in a study-specific Data Management Plan (DMP) prior to the start of the trial. All planned validation checks will be documented and described in a study-specific Data Validation Plan.

The electronic database is located at the Electronic Data Capture (EDC) system vendor. A validated electronic audit trail will track data entry and correction. All systems are validated and compliant to the Food and Drug Administration's ordinance 21 CFR part 11.

Protocol Code Number: SynAct-CS002

Adverse events, baseline findings, medical/surgical history will be coded using MedDRA terminology (version 18.0 or later). Medications will be encrypted using the ATC codes (Anatomical Therapeutic Chemical (ATC) Classification System). The processes used for coding will be specified in the DMP.

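### SAP 7.10 counts AE incidence by reported term in its text, while its own table makes that term listing-only and tabulates MedDRA terms by visit

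*SAP*

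**What the plan says.** The table in SAP 7.10 has two separate term variables. The CRF description, AETERM, is "Listing only (used for MedDRA coding". The coded variable, "AE MedDRA term (coding performed by DM"), is presented as the number of "patients and % /MedDRA term", by visit. No dictionary level is given for it.

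The text that closes the same section reads "The incidence of AEs will be summarized by the reported AE term". It then adds: "A subject will be counted only once in the incidence count for a specific AE term", even where the term has been reported several times for that subject.

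Protocol 24.6 commits to coding: "Adverse events, baseline findings, medical/surgical history will be coded using MedDRA terminology". SAP 3.7 waives coding for the interim analysis only.

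**The concern.** One part of the section keeps the reported term out of the summary tables and another part builds the incidence tables on it. Neither is said to govern. AEs are part of the primary safety objective (Protocol 12.1, SAP 2.1.1), and the safety analysis is descriptive (Protocol 23.4, SAP 3.1). No test stands behind the tables, so the tables are the safety result.

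If a programmer follows the text, an event described in different words at different sites occupies several rows. A reader comparing AP1189 with placebo for that event then sees several small percentages where one larger one belongs. The protocol's Phase 1 summaries show how easily near-synonyms arise: abdominal pain is listed for Part I (10.1.1) and an abdominal cramp for Part IV (10.1.6). Entered in those words on a CRF, they would be two rows.

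**Working it through.** The plan gives no figure to reproduce, so the check is mainly a comparison of texts.

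**1. What does the reported term mean?** The SAP 7.10 table distinguishes AETERM from the MedDRA term. The closing text speaks of a term being reported more than once for a subject. SAP 7.2 uses the word reported in the same way, for the medication name entered on the CRF. The plain reading is the term as entered.

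**2. Is the sentence limited to the uncoded interim?** It would suit the interim, where SAP 3.7 says AEs are not coded. But the interim used SAP version 1, and the sentence stands without restriction in version 2.0, which governs the final analysis.

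**3. Is a change explained anywhere?** SAP 3.12 lists the departures from the protocol, does not mention this one, and states that no others were identified. For this section, the revision history in Appendix 5 records only a corrected heading number.

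**4. Does the coded table supply the same information?** It is specified by visit, and the once-per-subject rule appears only in the closing text. For a given coded term, the number of distinct subjects affected lies between the largest single-visit count and the sum of the visit counts (capped at the group size). By-visit counts alone do not identify it.

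**5. How large could the split be?** Take n = 30, the minimum per treatment group proceeding to Part 2 (Protocol 23.2.1). Assume m = 6 subjects have the same event and that they divide evenly over k wordings, each subject using one wording. The 6 and the values of k are assumptions and come from neither document. Each row then shows (m/k)/n:

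| Wordings k | Subjects per row | Percentage per row |
|---|---|---|
| 1 | 6 | 6/30 = 20.0% |
| 2 | 3 | 3/30 = 10.0% |
| 3 | 2 | 2/30 = 6.7% |
| 6 | 1 | 1/30 = 3.3% |

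By coded term the result is 20.0% in every case. The number of subjects with any AE does not depend on how terms are grouped and is the same throughout.

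**The case against.** The strongest reply is that coded results are planned anyway. The table in SAP 7.10 provides patient counts per MedDRA term, the protocol commits to coding, and individual listings are planned for all safety variables (SAP 7). By-visit presentation also follows Protocol 23.4, which asks for safety summaries by treatment and time point. That is correct, and it means a coded table should exist. It does not give a once-per-subject incidence across visits, which is what the closing text sets out to define.

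A second reply is that the reported AE term may be loose wording for the coded term. That is possible, since the sentence does not name AETERM. But the table separates the two, and a programmer should not have to guess.

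Third, wording may vary little. Protocol 22.4 asks for a diagnosis or syndrome where known, and for one AE per cluster of signs. This should reduce variation, though it does not standardise terms. The sites are in Europe and Moldova, but neither document states the language in which AEs are entered, so no argument can rest on language.

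A reader might infer more than this: that final AE incidences will certainly be split, that every event is understated, or that the reported-term table is the only overall incidence. The documents do not support these readings. Splitting needs both the text to be applied literally and wording to differ. The table specifications are in Appendix 4, which is held separately and was not available; its shells may contain an overall coded summary. If they do, the closing sentence still disagrees with them.

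**Conclusion.** SAP 7.10 contradicts itself on the unit of AE incidence and should be corrected. On the text available, its once-per-subject incidence is by uncoded term, and the coded counts come only by visit. The consequence is conditional: per-event incidence is understated in tables built on the reported term, and only for events that sites word differently. In the illustration the loss runs from none (one wording) to 20.0% appearing as rows of 3.3% (six wordings); the real size cannot be known from the plan. Splitting can lower row percentages in any treatment group. No test, power or error rate is affected. The conclusion rests on reading the reported term as the CRF entry, and on the SAP text without its Appendix 4.

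**What to change.** In the closing text of SAP 7.10, replace the reported AE term with the MedDRA term, at preferred-term level and grouped by system organ class. Suggested wording:

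*In the final analysis, AE incidence is the number and percentage of subjects with at least one event, by MedDRA preferred term within system organ class and by treatment group. Each subject counts once per term over the AE reporting period defined in Protocol 22.4.*

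The preferred-term level is a proposal, since the documents name none. The period refers to the protocol's existing one, so no new AE window is introduced. Keep the by-visit table as supportive and AETERM in listings only, as the SAP table already has it. Check that the Appendix 4 shells agree.

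The cost is one SAP sentence and, if Appendix 4 lacks it, one table shell. Coding is already planned, so no new data are needed.
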